5.5 Premature Termination or Suspension of Study

This study may be suspended or prematurely terminated if there is sufficient reasonable cause. Written notification, documenting the reason for study suspension or termination, will be provided by the suspending or terminating party. If the study is prematurely terminated or suspended, the study principal investigator (SPI) will promptly inform the IRB and will provide the reason(s) for suspension or termination.

Circumstances that may warrant termination include, but are not limited to:

- Determination of unexpected, significant, or unacceptable risk to patients.
- Insufficient adherence to protocol requirements.
- Data that are not sufficiently complete and/or evaluable.
- Determination of futility.

6 STUDY SCHEDULE

National Dental PBRN orthodontists/dentist practitioners who opt to participate will be provided information and instructions pertaining to the study. These instructions will provide information for the practitioner(s) and staff who will help to execute the study. A detailed Practice Training Manual will be provided to each practice in hard-copy form prior to initiation of the study in the practice. The Practice Training Manual will carefully describe the patient selection procedures, methods for approaching patients and obtaining Informed Consent (according to regional approvals), methods for data collection, and other study procedures. In addition, RCs will conduct in-person or remote protocol training with office staff prior to initiating the study to make sure that they and their office staff understand the study procedures and have received instruction in completing CRFs.

The study will proceed in stages:

- 1) Each region will enroll approximately 35 practitioners who have completed IRB-mandated training into the study. Actual enrollment will be based on interest and enrollment into the Network, and likely will vary per region;
- 2) Practice personnel will receive necessary IRB training, and practitioners will undergo informed consent procedures as required by each region's IRB. Individual Investigator Agreements, the University of Alabama at Birmingham (UAB) Master Service Agreement and similar documents will also be obtained prior to the start of the study as required;
- 3) RCs will ensure practices are trained in the appropriate study procedures (see below sub-sections);
- 4) Practitioners will complete the Practitioner Characteristics Form;
The CC, along with the RAS and RCs, will coordinate the launch of the study. Once the RC has trained an office in the practice procedures, that practice should begin recruiting patients into the study immediately, or as soon as possible.
- 5) Practitioners and/or his/her designee who has completed human subject training will screen, consent and enroll eligible patients into the study.

An overview of study procedures to be completed at each study visit can be found in Appendix A.

6.1 Practitioner Screening/Enrollment

- Verify practitioner inclusion/exclusion criteria;
- Obtain and document consent from practitioner participant according to regional IRB requirements;
- Practitioner and applicable staff participate in training with RC;
- Practices will systematically search their current active patient lists to identify patients age 18 or older who are in active treatment for AOB who expect to have treatment completed within 24 months of enrollment into the study and meet study inclusion criteria;
- The maximum number (N) of patients from a single practitioner will be 15. If a practitioner has more than 15 potential patients, he/she should sequentially select the patients based upon their treatment start dates, beginning with the patient who started treatment the earliest. If some patients decline or withdraw, practitioners can move sequentially down the list to enroll up to 15 patients; and
- Practitioner completes Practitioner Characteristics data collection form.

6.2 Patient Enrollment/Baseline, Active Treatment Stage (Stage 1 [S1])

A potential patient may be recruited over the phone or at any visit when it is determined that a patient may be eligible for study participation. The designated office personnel will introduce the study to the patient and will ascertain that inclusion criteria are met. For patients who express interest in participating in the study, enrollment/baseline study procedures will occur during an in-office visit. Informed consent procedures and enrollment may occur during the same visit at which eligibility was confirmed.

- Verify eligibility and inclusion/exclusion criteria.
- Obtain and document consent from patient as required by IRBs.
- Obtain patient contact information and preferred method of contact (e.g., postal mail, email, telephone, text, other contacts).
- Patient and Practitioner complete Enrollment Visit data collection forms.
- Practitioner will obtain and upload initial cephalometric x-ray and intra-oral frontal photograph.

6.3 Retention Stage (Stage 2 [S2])

6.3.1 Appliance Removal, End of Active AOB Treatment: S2, Visit 1 (Complete within approximately 24 months after S1)

- Practitioner will obtain measurement of the height of right maxillary central incisor perpendicular to the incisal edges of the incisors.
- Practitioner will obtain intra-oral frontal photographs, one taken in maximum intercuspation, and another one taken with the incisors slightly apart.
- Practitioner will upload end of active treatment cephalometric x-ray and intra-oral frontal photographs.
- Patient and Practitioner will complete End of Active Treatment data collection forms.
- Verification of patient contact information and preferred method of contact.

6.3.2 Retainer Check Visits: S2, Visits 2-x (Varies; based upon retention visit intervals)

Information from routinely scheduled retainer check visits will be gathered during the first year after active treatment has terminated.

- Patient and Practitioner will complete Retainer Use data collection forms.
- Verification of patient contact information and preferred method of contact.

6.4 Final Study Visit (Stage 3 [S3]): Approximately 1-Year Post Appliance Removal (S2, V1 + 10 to 24 months)

- It will be acceptable to allow the Final Study Visit to occur as early as 10 months after appliance removal. The maximum limit for the timing of the final study visit will be 24 months post appliance removal or until end date of the study, whichever occurs first.
- Practitioner will obtain measurement of the height of right maxillary central incisor perpendicular to the incisal edges of the incisors.
- Practitioner will obtain and upload final intra-oral frontal photographs, one taken in maximum intercuspation, and another one taken with the incisors slightly apart.
- Patient and Practitioner will complete Final Study Visit data collection forms.
- Practitioner will provide final instructions to participant, if applicable.

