Population: The study will include approximately 840 adult National Dental PBRN practice AOB patients age 18 or older that are currently in active treatment, and **expect** to have treatment completed within 24 months of enrollment into the study.

Number of Sites: Approximately 210 National Dental PBRN practitioners.

Study Duration: Approximately 3.5 years

Subject Participation Duration: Approximately 3 years

Estimated Time to Complete Enrollment: Approximately 11 months

Schematic of Study Design:

Practitioner Screening/Enrollment

- Recruit, enroll, and train practitioners. Practitioner completes Practitioner Characteristics Form.

Patient Enrollment/Baseline, Active
Treatment Stage (Stage 1 [S1])

- At a routine orthodontic visit:
- Verify eligibility.
 - Obtain informed consent and assign subject ID.
 - Patient and Practitioner complete Enrollment Visit data collection forms.
 - Submit initial cephalometric x-ray and intra-oral frontal photograph.

Appliance Removal,
End of Active AOB Treatment
(Stage 2 [S2], Visit 1 [V1]; complete
within ~24 months after S1)

- At the time of appliance removal:
- Measure the height of the right maxillary central incisor.
 - Patient and Practitioner complete End of Active Treatment data collection forms.
 - Obtain intra-oral frontal photographs, one taken in maximum intercuspation, and another one with the incisors slightly apart.
 - Submit end of active treatment cephalometric x-ray and intra-oral frontal photographs.

Retainer Check Visits
(Stage 2, Visits 2-x; varies based
upon retention visit intervals)

- At the time of **each** routinely scheduled retainer check appointment:
- Patient and Practitioner complete Retainer Use data collection forms.

Final Study Visit (Stage 3 [S3])
(S2, V1 + 10 to 24 months)

- Approximately 1-year Post Appliance Removal:
- Measure the height of the right maxillary central incisor.
 - Patient and Practitioner complete Final Study Visit data collection forms.
 - Obtain intra-oral frontal photographs, one taken in maximum intercuspation, and another one with the incisors slightly apart.
 - Submit intra-oral frontal photographs.

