4 STUDY DESIGN

- This will be a prospective, observational 3.5-year cohort study of patients who are undergoing different types of orthodontic AOB treatment followed by retainers.
- The study population will consist of adult patients who are in active treatment for AOB, and expect to have treatment completed within 24 months of enrollment into the study. Approximately 210 orthodontists or dentists who routinely perform orthodontic treatment (approximately 35 in each of the six National Dental PBRN regions) will participate. Actual enrollment will be based on interest and enrollment into the Network, and likely will vary per region. Each practitioner will be requested to enroll approximately 3 - 8 adult patients in active AOB treatment over an approximate 11 -months enrollment period, with an enrollment goal of approximately 840 adult patients across the National Network. No practitioner will contribute more than 15 patients.
- Retrospective data will be collected to explore patient, practitioner, and dentofacial characteristics that influence the treatment recommendations and the accepted treatment plans for patients with AOB.
- The prospective cohort design will allow the investigation of how patient, practitioner, and dentofacial characteristics affect the success of treatment. The treatment provided to the patients will not be influenced at all by participation in the study.
- In addition, this study will allow the assessment of how treatment modalities, retainer regimens, and patient characteristics are associated with treatment stability and patient satisfaction one year after treatment.
- At each routinely scheduled retainer check visit, the patient will be asked to report on their retainer usage, and the practitioner will also be asked to judge retainer use.
- Patients will be asked again about satisfaction with their retainer regimen, as well as esthetics and function, at one year after treatment.
- Patients will participate in the study for approximately 3 years, on average, the duration of the treatment and follow-up phases. Practitioners' participation in the study will be approximately 3.5 years.

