5 STUDY ENROLLMENT AND WITHDRAWAL

5.1 Inclusion Criteria

Practitioner:

In order to be eligible to participate in this study, a practitioner must meet all of the following criteria:

- Is enrolled in the National Dental PBRN as a practitioner who is licensed in the United States (US), and does treat patients in the US on a recurring basis.
- Is a “full” participation level member, or willing to change from “information only” or “limited” to “full”.
- Is trained and certified in Human Subjects Protection Training.
- Is willing to complete study-specific training.
- Has attended or viewed a National Dental PBRN orientation session or has attended at least one annual regional meeting of practitioners.
- Is an orthodontist or a dentist that routinely performs orthodontic treatment.
- Has a sufficiently large patient population such that the practitioner estimates he/she can recruit approximately 3 - 8 adult patients in active treatment for AOB, and expect to have treatment completed within 24 months of enrollment into the study.
- Routinely takes cephalometric x-rays before and after treatment.
- Has the ability to upload (via internet) de-identified cephalometric x-ray and digital intra-oral frontal photographs to a central repository.
- Affirms that the practice can devote sufficient time in patient scheduling to allow focused recording of all data required for the study.
- Does not anticipate retiring, selling the practice, or moving during the study.

Patient:

The patient population will come from the National Dental PBRN practices participating in this study.

In order to be eligible to participate in this study, a patient must meet all of the following criteria:

- Must be at least 18 years of age.
- Must have AOB that is defined as one or more incisors that do not have vertical overlap with teeth in the opposing arch. The remaining incisors may have minimal incisor overlap, but none of them can contact teeth in the opposing arch.
This will be determined by examining the patient’s initial cephalometric x-ray, intra-oral photographs, and/or initial plaster or digital casts.
- Must be in active treatment for AOB, and expect to have treatment completed within 24 months of enrollment into the study.

- Must have an initial cephalometric x-ray (taken prior to the beginning of treatment). A cephalometric x-ray created from a cone-beam CT scan is acceptable.

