11.3 Final Analysis Plan

Analysis plan for Primary Objectives:

Primary objective #1 is to estimate the proportion of patients who are successfully treated. As described in section 3.2 (outcome measures), successful treatment is defined as occurring when patients have positive overlap at the end of treatment; this will be calculated with a 95% confidence interval.

Though not an explicit hypothesis, we expect those that are “successfully” closed will have had a smaller distance between the maxillary and mandibular incisor tips prior to treatment, i.e., at enrollment, than those not successfully closed. We will calculate the mean distance improved separately for those successfully treated and those not. It may be that those not successfully treated had more improvement than those who were successfully treated (if the former had a greater distance that needed to be corrected) and we want to capture this. Thus, as an additional but secondary measure of improvement, we will also calculate mean and median distance improved as descriptive measures.

Primary objective #2 is to estimate, among patients who are successfully treated, the proportion of patients whose treatment is stable. As described in section 3.2 (outcome measures), stability will be assessed one year after end of active treatment. The primary measure (strictest, most conservative classification) will be among patients who are determined to have been successfully treated at end of active treatment (having closed their AOB), what proportion of these have positive overlap at the one-year follow up time. This proportion will be estimated with a 95% confidence interval. Additional assessments of stability will include the proportion of all who had improvement in overbite (positive increases) during retention, no change in overbite during retention, and worsening of overbite (negative increases) during retention. We will calculate these mean and median changes as descriptive measures.

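### The one-year stability outcome accepts final visits from 10 to 24 months, and the stated durations (11 + 36 = 47 months against 42) leave late-enrolled patients with long remaining treatment too little follow-up

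*Protocol*

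**What the plan says.** Sections 3.1 and 3.2 place stability at one year after active treatment. For the primary measure, Section 11.3 asks, among patients successfully closed, "what proportion of these have positive overlap at the one-year follow up time". Section 6.4 allows the visit as early as 10 months after appliance removal. The latest date for the "final study visit will be 24 months post appliance removal or until end date of the study, whichever occurs first". The 10 to 24 month range also appears in the Protocol Summary schematic and in Appendix A.

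The predictor domains in Section 11.4.2 for objectives 3a and 3b are retainer regimen, treatment modality, dentofacial, patient and practitioner characteristics. For 3b, stability itself is added. Time since appliance removal is not listed.

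On the calendar, the Protocol Summary gives "Study Duration: Approximately 3.5 years", "Estimated Time to Complete Enrollment: Approximately 11 months" and "Subject Participation Duration: Approximately 3 years". Section 4 says "Patients will participate in the study for approximately 3 years, on average, the duration of the treatment and follow-up phases". The entry criterion in Section 5.1 is "Must be in active treatment for AOB, and expect to have treatment completed within 24 months of enrollment into the study". Section 11.2 allows 10% attrition by end of treatment and 20% by one year after it.

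**The concern.** There are two linked problems, both in text that the protocol itself fixes.

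First, the outcome is named for one time point, but the accepted visits run to twice that time. If relapse continues through the second year, a patient seen at 24 months has had more opportunity to relapse than one seen at 10, yet both enter the same proportion. Without a time term, the 3a and 3b models cannot separate a retainer or modality effect from a difference in visit timing.

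Second, the duration figures do not fit together, and the study-end cut-off turns that misfit into selective loss. The follow-up available to a patient shrinks month for month with later enrolment and with longer remaining treatment. Those who run out of calendar time are therefore not a random subset. The attrition allowance may cover their number, but it does not address who they are.

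**Working it through.** **Inputs.** Study duration 42 months, enrolment 11 months, participation about 36 months (Protocol Summary; Section 4 calls the last an average). Remaining treatment is expected to be at most 24 months (Section 5.1), which is an expectation and not a cap. The final visit falls 10 to 24 months after removal (Section 6.4). I start the 42 months at first patient enrolment; if they also cover practitioner recruitment and training, the shortfall is larger.

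**Can the stated 42 months be reproduced?**
- Enrolment + participation: 11 + 36 = 47.
- Last enrolled, 24 months' treatment, earliest permitted visit: 11 + 24 + 10 = 45.
- Same patient, one-year visit: 11 + 24 + 12 = 47.
- Same patient, latest visit in the window: 11 + 24 + 24 = 59.

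All exceed 42.

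**Available follow-up.** For enrolment month e and remaining treatment t it is 42 − e − t. With t = 24, the first patient enrolled has 42 − 0 − 24 = 18 months and the last has 42 − 11 − 24 = 7. A 10-month visit is out of reach when e + t > 32, and a 12-month visit when e + t > 30. A 24-month case must therefore enrol by month 8 to be seen at 10 months, and by month 6 to be seen at 12.

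**Share affected.** The protocol gives no distribution of remaining treatment, so t is an assumption; e is taken as uniform on 0-11. For t uniform on 0-24, the region e + t > 32 is a triangle of side 35 − 32 = 3, giving (3²/2)/(11 × 24) = 4.5/264 = 1.7%. For e + t > 30 the side is 5, giving 12.5/264 = 4.7%. The other rows follow in the same way.

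| Remaining treatment (assumed) | Cannot reach 10 months | Cannot reach 12 months |
|---|---|---|
| Uniform 0-24 | 1.7% | 4.7% |
| Uniform 12-24 | 3.4% | 9.5% |
| Uniform 18-24 | 6.8% | 19% |
| Uniform 0-30 (overruns) | 40.5/330 = 12% | 60.5/330 = 18% |
| All exactly 24 | 3/11 = 27% | 5/11 = 45% |

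**Effect of mixed visit times (illustration).** The protocol gives neither a relapse curve nor a visit-time distribution. Assume a constant relapse rate, S(t) = S(12)^(t/12), with 30% of visits at 18 months and 70% at 12.
- S(12) = 50%: S(18) = 0.5^1.5 = 35.4%. The mixture is 0.7 × 50 + 0.3 × 35.4 = 45.6%, a shift of 4.4 points.
- S(12) = 80%: S(18) = 0.8^1.5 = 71.6%. The mixture is 0.7 × 80 + 0.3 × 71.6 = 77.5%, a shift of 2.5 points.

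For scale, the table in Section 11.2 reproduces with a half-width of 5 points: 1.96² × 0.5 × 0.5/0.05² × (1 + 2 × 0.05) = 422.6, against 422 stated.

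**The case against.** The visit is planned for about one year. Offices are contacted every three months about coming one-year dates (Appendix D), and practitioners receive recall reminders (Section 5.3.1). A patient whose limit is 18 months will usually still be seen near 12, so the cut-off changes an on-target visit only when fewer than 12 months remain. Appendix D also puts the enrolment emphasis on the first 6 months, and 6 + 24 + 12 = 42 exactly. Front-loading would lower every figure in the table. The durations are all given as approximate. Analysis windows and sensitivity analyses are commonly left to a SAP, which is not shown. The relapse illustration rests on assumed inputs, and visits at 10 or 11 months would pull the estimate the other way.

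Most of this stands as a limit on size. It does not remove the conflict. Five months in 42 is more than rounding, and an analysis plan cannot supply missing calendar time. As written, a 24-month status counts as one-year status.

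Three stronger readings are tempting, and the documents do not support them:
- That the longest cases have no one-year outcome. Loss needs long remaining treatment and late enrolment together.
- That modalities with longer treatment will look more stable because they are seen earlier. Patients enrol while already in treatment, so the limit depends on remaining and not total treatment, and nothing in the protocol links modality to remaining treatment.
- That the loss exceeds the 20% attrition allowance. Among the cases above, that happens only when every patient has the full 24 months left. Ordinary attrition would, however, come on top of the other figures.

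**Conclusion.** The point holds in a limited form. The outcome time and the accepted visit window disagree. The stated study duration is 5 months short of enrolment plus participation, and 3 months short (45 against 42) of even the earliest permitted visit for the last-enrolled 24-month case.

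The share who cannot be seen in time depends on an unstated distribution. It is probably small if remaining treatment is spread over 0-24 months, and material if treatment overruns or clusters near the maximum. The loss is selective for late enrolment combined with long remaining treatment. Bias between modalities is a risk, with no direction established. Mixed visit times could use up most of the 5-point margin at 50% stability and about half of it at 80%, under the assumed constant relapse rate and visit mix. If relapse is mostly early, the effect is smaller. This should be corrected, but it does not undermine the study.

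**What to change.** 1. Reconcile the duration figures in the Protocol Summary and Section 4. About 47 months are needed for every patient who finishes treatment within 24 months to reach a one-year visit. If 42 months is kept, state the expected loss and the assumption about remaining treatment behind it.
2. Add months since appliance removal to the 3a and 3b models in Section 11.4.2. It comes from two visit dates already recorded.
3. In Section 11.3, report the stability proportion for visits close to 12 months, in a window fixed before the data are examined, alongside the proportion for all final visits and the distribution of visit times.

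The cost is slightly more analysis and a less precise near-12-month estimate, because late visits leave it. Late attenders may differ from others, which is why both proportions should be shown. I would not tighten eligibility by expected removal date: that would turn a possible loss of late-enrolled, long-remaining cases into a certain exclusion.
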